## 15 Recruitment

The 4 RAAM clinics serve the entire North Simcoe Muskoka Local Health Integrated Network region, are owned and operated by the Royal Victoria Regional Health Centre and are administered by the same manager and medical lead (see Section 9 for details).

Each RAAM clinic will screen 100% of patients who successfully complete induction and stabilization with Suboxone® as this is the point at which patients might be eligible for enrollment and randomization. Screening will continue until the target population is achieved. There will be no fixed number of patients that must be recruited from any site, only that each

site will have a 1:1 allocation ratio between the treatment groups. The expectation is that 1 to 2 patients will be enrolled per week.

The RAAM clinic healthcare providers will be responsible for expressed consent in eligible patients. For those patients who provide expressed consent, the RAAM clinic healthcare providers will contact the study team and provide them with the patient's name and contact number and inform the patient that they will be contacted by the study team to further discuss the study. A study team member will contact the patient and arrange a meeting, either in person, telephone or videoconference, to determine eligibility and review the study and secure informed consent.

For patients who cannot travel to a laboratory to complete their screening bloodwork or electrocardiogram, arrangements will be made to have the screen completed at their home address at no charge to the patient.

Patients who are enrolled in the study at the Midland, Orillia, and Wasaga Beach RAAM clinic sites will now be able to receive their Sublocade® doses on-site. Previous to this study, those patients would have had to travel to the Barrie RAAM clinic site to receive Sublocade®. A taxi ride for this travel would be required as there is no bus or train that connects these sites, with the cost for a round trip in excess of \$150 (CDN) (personal communication, [name]).

## 16 Allocation

### 16.1 Sequence generation

Participants will be randomly assigned to either Suboxone® or Sublocade® with a 1:1 allocation schema as per a computer-generated randomisation schedule stratified by RAAM clinic site and severity of OUD (moderate versus severe by DSM-V criteria) using permuted blocks of size 6 in each strata. A single block size was chosen since the next block size of 18 might be too large to allocate patients in a 1:1 ratio in the smaller RAAM clinics. The block size will not be disclosed to ensure concealment. Sufficient numbers of blocks will be prepared *a priori* to ensure sufficient coverage for all strata in the event that they have different sample sizes as there will be no *a priori* fixed ratio for enrollment in the different strata.

### 16.2 Concealment mechanism

The random allocation sequence will be generated using the *ralloc* function in STATA 17/MP for Mac by an independent statistician not associated with the trial. This allocation sequence will be uploaded into and accessed from REDCap®, which is an on-line, password-protected, web-based research electronic database system stored on the PHIPA-protected servers at the Royal Victoria Regional Health Centre. Allocation concealment will be ensured as the study coordinator will not release the randomisation code until the patient has been recruited into the trial, which will only take place after all baseline screening measurements have been

completed. The randomisation schedule will only be accessible by independent study coordinators not associated with this study to ensure that randomisation will be conducted without any influence of the principal investigators, RAAM healthcare providers, or other study personnel.

### 16.3 Implementation

Expressed consent for the study will be obtained by the RAAM clinic healthcare providers. Informed consent will be obtained by the study team. All patients who give consent for participation and who fulfil the inclusion criteria will be randomized. Randomization will be requested by the study team member who secured informed consent from an independent study coordinator who is not associated with the study by calling a centralized study telephone number. The study coordinator will access the random allocation sequence through REDCap®, and then inform the study team member who secured informed consent of the treatment allocation for this patient. The study team member will subsequently inform the RAAM clinic healthcare provider who would then provide the information about treatment allocation to the patient. All RAAM clinic healthcare providers will be made aware of the treatment allocation as this is an open-label study.

## 17 Masking

This is an open-label, pragmatic, comparative effectiveness study so neither participants nor RAAM healthcare providers nor study personnel, including data analysts, will be masked to the allocation.

## 18 Data collection

### 18.1 Methods

All data will be collected by centrally trained RAAM clinic healthcare providers and study personnel. All **routinely collected data** will be collected by the RAAM clinic healthcare providers and stored in MEDITECH Expanse, the electronic health record system used across all the study RAAM clinics and the Royal Victoria Regional Health Centre. This routinely collected data will be extracted by study personnel and stored in electronic case report forms created in REDCap®. All study-specific data will be collected by study personnel and stored in electronic case report forms created in REDCap®.

#### 18.11 Routinely collected data

##### *18.11a Prior to induction*

For all RAAM clinic patients with OUD who are eligible to receive any opiate substitution therapy, the following demographic and baseline clinical and laboratory data are collected **prior to induction** with any treatment (Table):

Data	Description	Data type
Demographics		
Date of birth	Month/day/year	Mm/dd/yyyy
Sex at birth	Male: Female	Categorical
Pregnant	Yes: No	Categorical
Ontario health insurance plan number	Unique provincial insurance number assigned to every resident	xxxx-xxx-xxx-version code
Ontario drug plan status	Insured versus non-insured	Categorical
Residency	Homeless; transient (< 6 months at same address, couch surfing or shelter); stable (≥ 6 months at same address)	Categorical
Children in home	Yes: No	Categorical
Children ages	Years	Continuous
Telephone contact	Yes: No	Categorical
Number		(xxx)-xxx-xxxx
Employment status 	Full-time (≥ 40 hours per week for ≥ 90 days per year); Part-time (≤ 40 hours per week or ≥ 90 days per year); Casual (≤ 90 days per year); unemployed	Categorical
Incarceration 	Incarceration in ≤ 12 months (Yes: No)	Categorical
Race 	White: Non-white, non-indigenous: Indigenous	Categorical
Clinical		
OUD diagnostic screen	≥ 2 of 11 DSM-V criteria must be present ≤ 12 months for diagnosis of OUD	Categorical: range 0 to 11:
OUD severity	DSM-V criteria of mild, moderate or severe OUD	Categorical: mild (2-3 criteria); moderate (4-5 criteria); severe (≥6 criteria)
Medical history	Comorbid illness screen, including mental health and substance use	Categorical
Medications	Prescribed	Categorical

Alcohol use	Yes: No	Categorical
Opioid use	Type: Route	Categorical
Other substance use	Type: Route	
Recent substance/opioid use	Timeline Followback questionnaire (assesses use and frequency of use of substances over the previous 7 days)	Categorical
Hospitalization	Substance-related $\leq$ 12 months (includes emergency room visit, admission to hospital, mental health or detoxification facility) (Yes: No)	Categorical
General physical exam	Vital signs; height; weight	Continuous
Opioid withdrawal screen	$\geq$ 3 of the following: dysphoria; nausea or vomiting; muscle aches; lacrimation or rhinorrhea; pupillary dilation or piloerection or sweating; diarrhea; fever; insomnia; yawning	Categorical; range 0-9
Jaundice	Yes: No	Categorical
Mental status	Glasgow coma scale	Categorical (range 3-15)
Opiate Craving Visual Analog Scale	Score $\geq$ 21 suggests clinically significant craving	Continuous (range 0-100)
Clinical Opiate Withdrawal Scale	Score $\geq$ 13 suggests clinically significant withdrawal	Continuous (range 0-48)
Laboratory		
Pregnancy	b-hCG assay (Yes: No)	Categorical
Liver	AST, ALT	Continuous
	Hepatitis virus serology	Categorical
Urine toxicology	Section 12.11a for description	Categorical
Renal	Creatinine	Continuous

 Employment status, incarceration and race are routinely collected in treatment studies for OUD as they have been identified as risk factors for outcome differences.

 All laboratory and electrocardiogram measurements and interpretations done at *LifeLabs™*

#### 18.11b During treatment

Data	Description	Data type
------	-------------	-----------

Urine toxicology	Section 12.11a for description	Nominal
Recent substance/opioid use	Timeline Followback questionnaire (assesses use and frequency of use of substances over the previous 7 days)	Categorical
Counselling	Individual patient counselling for OUD, mental health and trauma	Narrative
General exam	Vital signs: Glasgow coma scale:	Continuous
Pregnancy	b-hCG assay (Yes: No)	Categorical
Bloodwork (optional)	Electrolytes: Liver: Renal	Continuous
Buprenorphine breakthrough dosing	Extra buprenorphine dosed for breakthrough	Continuous
Compliance	Missed appointments or doses (Yes: No)	Categorical
Hospitalization 	Any Royal Victoria Regional Health Centre emergency room visits, admissions to hospital or mental health or detoxification centre since previous clinic visit (Yes: No)	Categorical
Reason for visit/admission	Opioid-related (Yes: No)	Categorical
Serious adverse events 	Hospitalization (for any reason)	Categorical
Reason	Opioid-related (Yes: No)	Categorical

 Only hospitalization events associated with the Royal Victoria Regional Health Centre are accessible to the RAAM clinic healthcare providers as the clinics share the same electronic health record system as previously described. All other hospitalizations would have to be self-reported by the participants and consent for access to the health records would then need to be secured by the RAAM clinic healthcare providers.

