## 9 Study Setting

The four RAAM clinics in the North Simcoe Muskoka Local Health Integrated Network will recruit patients for the study. The North Simcoe Muskoka Local Health Integrated Network is a provincial regional health authority mandated to plan, integrate and fund local health services across the District of Muskoka, Simcoe County and Grey County. This region serves a population of 479 471 (2015), representing 3.5% of the province of Ontario's population. The Network distributes over \$880 million (CDN) in funding to 61 unique health service provider organizations that include 7 hospitals, 21 long-term care homes, 3 community centres, 23 community support services and 7 community health centres. In partnership with the Simcoe Muskoka District Health Unit, the Network developed the Simcoe Muskoka Opioid Strategy in 2017 in response to the higher-than-average provincial rates of opioid-related morbidity and mortality being experienced in the region. Increased access to OAT through the RAAM clinics is an essential component of that strategy (p.38).

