#### 12.12 Healthcare utilization

Difference in incidence rates of healthcare days at 12-months from the date of randomization, where **healthcare days represent the number of days alive and registered for an emergency room visit or admitted to an acute care or mental health facility for opioid-related harms or poisonings**. For each group, the incidence rate is calculated by dividing the total number of healthcare days by the total person days exposure over the study period. The potential number of healthcare days for each patient is the number of days alive during the 12-month study period, with the maximum being 365 days. Any day in which a patient is documented to have had an emergency room visit or is admitted to an acute care or mental health facility for any opioid-related harm or poisoning will be counted as a healthcare day. To estimate the number of opioid-related harms and poisonings resulting in healthcare utilization, the Discharge Abstract Database, Ontario Mental Health Reporting System database, National Ambulatory Care Reporting database, Registered Persons Database, and Office of the Registrar General of Ontario database will be linked to each patient's Ontario Health Insurance Plan number and the following opioid-related harms and poisonings International Statistical Classification of Diseases and Related Health Problems, Tenth Revision, Canada (ICD-10-CA) codes will be used to estimate the number of healthcare days utilized during the study period: Y45, F11.0-F11.9, T40.0-T40.4, T40.6. All opioid-related harms and poisonings resulting in the utilization of a healthcare day regardless of intent (ICD-10-CA X42 (accidental), ICD-10-CA X62 (intentional), and ICD-10-CA Y12 (undetermined)) will be included in the final analysis. Only those healthcare days in which opioid use was considered to be influential to the ER visit or hospitalization will be included and are identified by the following ICD-10-CA codes: M (most responsible diagnosis), 1 (pre-admit comorbidity), 2 (post-admit comorbidity), W or X or Y (Service transfer diagnosis). In addition, Diagnostic and Statistical Manual of Mental Disorders, 5th Edition codes 304.00 and 305.50 will be used to capture healthcare days for opioid-related harms and poisonings.

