## 22 Harms

In this pragmatic, comparative effectiveness study, the RAAM clinic healthcare providers will document adverse events that occur during the study according to their clinical judgement and

usual standard of care. The subsequent clinical decisions and actions to any adverse event will be left up to the discretion of the healthcare providers. The only adverse event that will be considered serious will be any healthcare utilization for any reason during the 12-month study period, defined as any emergency room visit, admission to hospital, mental health facility or detoxification centre. Screening for these events will occur with each clinic visit by soliciting the information from the participant but will also occur unsolicited by screening the electronic health record system between visits. These healthcare utilization events will be reported to the Trial and Data management committees on a quarterly basis, along with the Research Ethics Board according to local regulatory standards.

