## 26 Consent

This pragmatic, comparative effectiveness study involves the random assignment of Sublocade® or Suboxone® to participants who meet the Health Canada-approved indications for their use. This study fulfils the criteria for a low intervention clinical trial in that the drug treatments are Health Canada-approved, the drug treatments are being used in accordance with the terms of the Health Canada-marketing authorization, and any additional study-related assessments (Medication Satisfaction and WHOQOL-BREF questionnaires) and follow-up (12-month healthcare utilization) do not pose more than minimal additional risk or burden to the safety of the participants compared with normal clinical practice. As such, eligible participants will be briefly informed by their RAAM clinic healthcare providers about the main features of the trial that are not part of the usual standard of care, notably, randomisation; the Medical Satisfaction and WHOQOL-BREF questionnaires, and healthcare utilization follow-up at 12-months from enrollment. A **modified** written informed consent describing **only** the process and rationale for randomization and the description, need for and schedule of the Medication Satisfaction and WHOQOL-BREF questionnaires will be obtained prior to enrolment by the Principal investigators or their nominated delegates. The written informed consent will not contain any information about the study drugs, administration, side effects or duration of treatment as verbal consent will be obtained by the healthcare providers as part of the usual standard of care. In addition, the written informed consent will not contain any information about the 12-month healthcare utilization follow-up as this is routinely collected data that will be de-identified and analysed in aggregate thus posing no additional burden or risk to the safety of the participants.

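### Non-opioid serious events at other hospitals have no described capture route once a patient stops attending, so serious-event counts will be incomplete

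*Combined protocol and SAP*

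**What the plan says.** Section 22 recognises one kind of serious adverse event: "any healthcare utilization for any reason during the 12-month study period". It spells this out as an emergency room visit or an admission to a hospital, mental health facility or detoxification centre. Two detection routes are named. The first is direct questioning: "Screening for these events will occur with each clinic visit by soliciting the information from the participant". The second is a search of the electronic health record between visits.

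The footnote in Section 18.11b, repeated in 18.12, limits the second route: "Only hospitalization events associated with the Royal Victoria Regional Health Centre are accessible to the RAAM clinic healthcare providers". For everything else, "All other hospitalizations would have to be self-reported by the participants and consent for access to the health records would then need to be secured". The hospitalization item in both tables names only the sponsor's hospital. The serious-event item in both tables says hospitalization for any reason and does not mention emergency visits.

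A separate provincial linkage by health insurance number is planned for the second primary outcome (12.12 and 18.13). Section 12.12 lists opioid codes and adds: "Only those healthcare days in which opioid use was considered to be influential to the ER visit or hospitalization will be included". Section 18.13 keeps the linked records inside a secure environment and refers back to 12.12 for what is collected.

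Section 9 counts "7 hospitals, 21 long-term care homes" among the region's providers and places the sponsor's hospital in Barrie. Three of the four clinics are in other towns.

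**The concern.** The definition of a serious event is broad and the means of finding one are narrow. A patient from the Orillia, Midland or Wasaga Beach clinic may well use a hospital other than the sponsor's. Section 15 notes that no bus or train links those sites to Barrie. If that patient has stopped attending, nobody asks about the event, and the record screen cannot see it. If it is not opioid-coded, the linkage as described does not count it.

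These counts go to the trial and data management committees each quarter and to the ethics board, and any published safety statement would draw on them. Section 20 plans no analysis of serious events, so nothing there would reveal or correct the shortfall. If attendance also differed between arms, the shortfall would differ too, and an apparent safety contrast could arise from follow-up alone.

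**Working it through.** The plan states no figure for serious-event capture, so there is nothing to reproduce. The first step is to set the routes side by side.

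| Event | Patient still attending | Patient no longer attending or withdrawn |
|---|---|---|
| Any cause, sponsor's hospital | Record screen and questioning (22, 18.11b) | Record screen |
| Opioid-coded emergency, acute or mental-health event, other hospital | Self-report; linkage (12.12) | Linkage, for the primary outcome |
| Non-opioid event, other hospital | Self-report | None described |
| Detoxification-centre admission outside the sponsor's system | Self-report | None described; not named in 12.12 or 18.13 |

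The right-hand column will not be empty. Section 18.22 lets providers withdraw patients for missed visits, and Section 14.3 allows for loss to follow-up of up to 50%. Section 18.22 promises continued follow-up of withdrawn patients from routinely collected data, but outside the sponsor's hospital the routine item depends on a visit. Section 19 also names the electronic record as a source for utilization. Section 18.1 shows that this is the system shared by the clinics and the sponsor's hospital, so it adds no reach.

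The second step is an illustration of size. Let

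- s = share of serious events that can be found only by self-report;
- c = share of follow-up time in clinic contact;
- r = probability that such an event is reported when the patient is in contact.

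Share captured = (1 − s) + s × c × r.

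The documents give none of the three, so all values are assumptions. If opioid-coded events elsewhere were added to the safety counts from the linkage, s would be smaller.

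Equal contact in both arms, c = 0.8:

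| s | r = 0.9 | r = 0.6 |
|---|---|---|
| 0.2 | 0.8 + 0.2 × 0.72 = 0.944 | 0.8 + 0.2 × 0.48 = 0.896 |
| 0.5 | 0.5 + 0.5 × 0.72 = 0.860 | 0.5 + 0.5 × 0.48 = 0.740 |
| 0.8 | 0.2 + 0.8 × 0.72 = 0.776 | 0.2 + 0.8 × 0.48 = 0.584 |

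The between-arm ratio is then 1.00: counts are too low, but equally so.

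Unequal contact, equal true rates, ratio = capture in the better-attending arm ÷ capture in the other:

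- c = 0.9 versus 0.75: from 0.908 ÷ 0.890 = 1.02 (s = 0.2, r = 0.6) to 0.848 ÷ 0.740 = 1.15 (s = 0.8, r = 0.9).
- c = 0.8 versus 0.5: from 0.896 ÷ 0.860 = 1.04 to 0.776 ÷ 0.560 = 1.39, at the same two settings.

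These ratios show only how the mechanism behaves. Either arm could be the better-attending one.

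**The case against.** Several points on the other side are sound.

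- **Consent.** A reader might infer that an outside event is lost unless the patient later agrees to release records, and that the consent form causes this because "the written informed consent will not contain any information about the 12-month healthcare utilization follow-up". The documents do not support that. The permission in 18.11b is for access to records, so it bears on verification; a self-reported event is already known. The omission in Section 26 is justified there by the use of routinely collected, de-identified data analysed in aggregate, which is the linkage. Section 26 also has patients told verbally about the utilization follow-up.
- **Missed visits.** The hospitalization item covers the time since the previous visit, so one missed visit need not lose an event. The loss falls on patients who leave clinic contact.
- **Linkage scope.** Section 12.12 defines what counts in the outcome, not the data cut. The research plan attached to the linkage letter (34.6) is not in the text, and a wider cut may already be planned. The supportable statement is that no route is described, not that none exists.
- **Direction of bias.** It is tempting to say that the injection arm will attend more, because injections are given in clinic while the comparator can move to take-home doses (11.1). But the timeline in Section 13 is the same for both arms, and Section 5.3 ties longer take-home intervals partly to clinic attendance. A difference could run either way or be absent.
- **Purpose.** No objective compares all-cause harm, both drugs are approved, and the access limit is stated openly.
- **Form wording.** The hospital's name in the hospitalization item could be read as qualifying only emergency visits. Emergency visits elsewhere would still be left out.

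The gap remains after all of this. Section 22 deliberately includes non-opioid events, and reminder calls and the nurse's contact number (11.5, 18.21) are not given the task of collecting them.

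**Conclusion.** The concern holds for a defined group: non-opioid serious events at other hospitals, and detoxification admissions outside the sponsor's system, in patients who stop attending or are withdrawn. No capture route is described for them, so serious-event counts will fall short of the Section 22 definition. The shortfall cannot be sized from the documents; under the assumed values with equal attendance, capture runs from 58% to 94%.

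Bias between arms is a possibility that depends on unequal attendance, which the trial itself treats as an outcome (12.23). It is not a demonstrated effect. A reader might take the 20% and 50% loss figures in 14.3, give one to each arm, and quote the resulting ratio as an expected bias. Those figures are a cited study's rate and this trial's worst case, two alternatives for one quantity, so they do not describe a contrast between arms.

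Nor should the point be extended to the primary utilization outcome. Opioid-coded emergency, acute and mental-health days are counted through the linkage whatever the attendance. This is an inexpensive improvement to safety ascertainment, not a threat to the primary result.

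**What to change.** 1. In 12.12 and 18.13, extend the linked data request to all-cause emergency visits, acute and mental-health admissions, and deaths, for every randomised patient. The opioid-coded primary outcome keeps its definition.
2. In Section 20, add a by-arm table of all-cause events from that source. Clinic-reported events stay in use for real-time review, since the linked records cannot leave the secure environment.
3. In 18.11b and 18.12, reword the hospitalization and serious-event items to match Section 22: any facility, emergency visits included. Detoxification-centre admissions must still be collected at the clinic, because the linkage does not name those centres, and they will remain incomplete for patients who leave. The report should say so.

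Asking at enrolment for permission to obtain outside records is an optional aid to verification.

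Cost: the linkage is already planned and budgeted at $12 587 (Section 35). The linkage letter (34.6) says the quote can change with scope, and Section 3 says no study funding is currently available, so the wider request needs a revised quote before it is adopted. Beyond that, the change adds one table and a revision of two form items.
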